1.1 Background Information

This study will evaluate the effectiveness of refractive correction alone for the treatment of previously untreated strabismic or combined-mechanism amblyopia in children 3 to <7 years old with visual acuity of 20/40 to 20/400.

A recently completed PEDIG study (ATS5) found that in 3 to <7-year-old children with previously untreated anisometropic amblyopia, refractive correction alone improved visual acuity by 2 or more lines in 77% of the patients and amblyopia resolved in at least one third of the patients.¹ These results supported previous observations from retrospective and pilot studies²⁻⁵ as well as Stewart et al's prospective report⁶ on 18 children with anisometropic amblyopia whose visual acuity improved after treatment with spectacle correction only.

Improvement in amblyopic eye visual acuity from treatment with optimum refractive correction in cases of anisometropic amblyopia is plausible because the refractive correction treats the underlying amblyogenic condition (i.e., uncorrected unequal refractive error) by providing retinal images of more similar clarity, size, and contrast. Elimination of the dissimilar retinal images, which may act as barriers to normal visual input, allows the amblyopic eye to receive appropriate visual stimulation. In contrast, visual acuity improvement with refractive correction alone in cases of amblyopia associated with strabismus is not expected to occur when the refractive correction does not completely eliminate the strabismus and restore fusion. In such cases, the underlying amblyogenic factor of a manifest ocular deviation remains; consequently, active cortical inhibition is presumably still present. Nonetheless, Stewart and colleagues recently reported finding gains in amblyopic eye visual acuity of children with strabismic and combined-mechanism amblyopia after a period of treatment with refractive correction alone.⁶ The PEDIG also observed this to occur in a subgroup of children with previously untreated strabismic and combined-mechanism amblyopia in a recent study.⁷ Amblyopic eye acuity improved by ≥ 2 lines from spectacle-corrected baseline acuity in 9 (75%; 95% CI = 43% - 95%) of the 12 patients with strabismic amblyopia and in 9 (69%, 95% CI = 39% - 91%) of the 13 patients with combined-mechanism amblyopia. Mean change from baseline to maximum improvement was 2.2 ± 1.8 and 2.6 ± 2.0 lines, respectively. These results are similar to those of Stewart and colleagues⁶ who reported visual acuity improvement averaging 3.0 lines in 16 children with strabismic amblyopia and 1.9 lines in 31 children with combined-mechanism amblyopia.

Although our results support the suggestion of Stewart et al.⁶ that strabismic amblyopia can improve with spectacle correction alone, they are not conclusive because both studies had small numbers of patients. Also, our classification of strabismus was based on alignment without refractive correction. Thus, a larger controlled study is needed to confirm or refute these findings in patients with strabismic and combined-mechanism amblyopia.

The ideal study design to answer the question of whether spectacles alone can significantly improve amblyopic eye visual acuity in strabismic children is a randomized trial with a control group who does not receive optical correction. However, most pediatric eye care providers would be reluctant to randomize esotropic children with hyperopic refractive error to a control

154 group of no optical correction because of the likelihood of some children having
155 accommodative esotropia, which would necessitate that hyperopic spectacles be prescribed.
156 The number of esotropic amblyopes without an accommodative component is sufficiently few
157 to make a randomized trial not feasible. Therefore, we have chosen to perform an observational
158 study with a large number of children with pure strabismic and combined-mechanism
159 amblyopia in order to evaluate the effect of refractive correction in this population of patients.
160

161 **1.2 Study Objective**

162 To evaluate the effectiveness of refractive correction alone for the treatment of previously
163 untreated strabismic or combined-mechanism amblyopia in children 3 to <7 years old.
164

165 **1.3 Synopsis of Study Design**

166 Major Eligibility Criteria (*see section 2.2 for a complete listing*)

- 167 • Age 3 to < 7 years
- 168 • Amblyopia associated with strabismus (with or without anisometropia)
- 169 • Visual acuity in the amblyopic eye between 20/40 and 20/400 inclusive through best
170 refractive correction
- 171 • Visual acuity in the sound eye 20/40 or better and inter-eye acuity difference ≥ 3
172 logMAR lines through best refractive correction
- 173 • Refractive error meeting at least 1 of the following criteria: $\geq 1.00D$ of astigmatism in
174 the amblyopic eye, $\geq 1.00D$ spherical equivalent anisometropia, or $\geq +2.00D$ spherical
175 equivalent hyperopia in either eye
- 176 • No prior amblyopia therapy
- 177 • No previous spectacle wear
- 178 • Investigator wishes to prescribe spectacles for refractive correction
179

180 Treatment

181 Patients will receive spectacles to correct their refractive error.
182

183 Visit Schedule

[figure not shown]
- 184 • Baseline exam
- 185 • Visit A: 9 weeks ± 10 days
- 186 • Visit B: 18 weeks ± 10 days (outcome exam by ATS certified examiner)
- 187 • 9-week Follow-up Exams: every 9 weeks ± 10 days (if needed- *section 4.5*) until amblyopia
188 resolves or until visual acuity does not improve at least 1 line (confirmed by a retest using a
189 $-1.00D$ lens over spectacles) from the previous study visit (*section 4.5*).
190

191 At each visit, distance visual acuity will be assessed in each eye, and ocular alignment and
192 stereoacuity testing will be performed.
193

194 Primary Analysis

195 As defined in the analysis plan, separate analyses will be conducted for three patient subgroups
196 based on the proposed mechanisms of visual acuity improvement. The proportion of patients in
197 these groups with 2 or more lines improvement in amblyopic eye visual acuity will be
198 calculated and exact 95% confidence intervals will be computed. Point estimates and 95%
199 confidence intervals for the mean lines of improvement in amblyopic eye visual acuity from
200 baseline to the 18-week outcome exam will also be calculated. For each patient, the maximum
201 acuity (at 18 weeks or after) and the visit at which this occurred will be determined. Analysis of
202 visual acuity at this last visit will parallel the analysis done on visual acuity at 18 weeks.

1.4 Study Summary Flow Chart

CHAPTER 2: SCREENING & PATIENT ENROLLMENT

2.1 Eligibility Assessment and Informed Consent

A patient is considered for the study after undergoing a routine eye examination (by a study investigator as part of standard care) that identifies amblyopia meeting the eligibility criteria.

For patients who appear eligible for the study following a “standard-care” or preliminary examination, the study will be discussed with the child’s parent(s) or guardian(s) (referred to subsequently as parent(s)). Parent(s) who express an interest in the study will be given a copy of the informed consent form to read. Written informed consent must be obtained from the parent prior to performing any study-specific procedures that are not part of the patient’s routine care.

2.2 Eligibility and Exclusion Criteria

The following criteria must be met for the patient to be enrolled in the study:

1. Age 3-<7 years
2. Able to perform visual acuity testing using the ATS single-surround HOTV protocol
3. Amblyopia associated with strabismus (comitant or incomitant) with or without anisometropia
 - At least one of the following criteria must be met:
 - Heterotropia at distance and/or near fixation on examination (without spectacles)
 - History of strabismus surgery (or botulinum toxin extraocular muscle injection)
 - Documented history of strabismus that is no longer present (and which in the judgment of the investigator is the cause of amblyopia)
4. Visual acuity measured in each eye according to the procedures described in *section 2.3.2* that meet the following criteria:
 - Amblyopic eye 20/40 to 20/400 inclusive
 - Sound eye $\geq 20/40$
 - Inter-eye acuity difference ≥ 3 logMAR lines (i.e., amblyopic eye acuity at least 3 logMAR lines worse than sound eye acuity)
5. No previous spectacle correction
6. Refractive error meeting at least 1 of the following criteria: $\geq 1.00D$ of astigmatism in the amblyopic eye, $\geq 1.00D$ spherical equivalent anisometropia, or $\geq +2.00D$ spherical equivalent hyperopia in either eye.
7. Investigator wishes to prescribe spectacles to correct refractive error
8. No prior amblyopia treatment
9. No current vision therapy or orthoptics
10. No ocular cause for reduced visual acuity
 - Nystagmus per se does not exclude the patient if the above visual acuity criteria are met
11. Ocular examination within 2 months prior to enrollment
12. Cycloplegic refraction within 2 months prior to enrollment
13. No myopia ($\geq -0.25D$ spherical equivalent)
14. No prior intraocular or refractive surgery
15. No strabismus surgery planned in the 9 weeks following the Baseline Visit
16. Parent understands protocol and is willing to accept treatment
17. Parent has home phone (or access to phone) and is willing to be contacted by Jaeb Center staff
18. Relocation outside of area of an active ATS site within next 6 months not anticipated

251 **2.3 Screening Examination Procedures**

252 **2.3.1 Historical Information**

253 Historical information elicited will include the following: date of birth, gender, race, ethnicity, prior
254 amblyopia therapy (e.g., glasses, patching, pharmacologic, filters), and spectacle correction.

256 **2.3.2 Testing Procedures**

257 1. Ocular Alignment Testing: Ocular alignment at distance and near will be assessed with the
258 cover/uncover test to determine if a tropia is present; if present, it must be determined
259 whether the frequency is constant or intermittent.

- 260 • Strabismic deviations will be measured first with the Simultaneous Prism and Cover
261 Test (SPCT) and then by the Alternate Prism and Cover Test (APCT) in primary
262 position at distance and near using the methods as outlined in the ATS Testing
263 Procedures Manual. The SPCT measurements should always be performed before
264 the APCT measurements.
- 265 • Testing must be performed prior to cycloplegia.
- 266 • Measurements made using the Krimsky test are NOT allowed.
- 267 • Testing must be performed no more than 7 days prior to enrollment.

268
269 2. Visual Acuity Testing: Visual acuity testing will be done by a certified examiner using the
270 ATS single-surround HOTV letter protocol on the Electronic Visual Acuity Tester. The
271 protocol for conducting visual acuity testing is described in the ATS Testing Procedures
272 Manual. Aspects of the testing protocol that are specific to this study are:

- 273 1. Testing is performed with the optimal refractive correction (*section 2.5*) as
274 determined from a cycloplegic refraction completed no more than 2 months prior.
- 275 2. Testing can be performed without cycloplegia or after cycloplegia when the child is
276 sufficiently attentive for this to be accomplished (*although it is preferable that*
277 *testing be done without cycloplegia*).
- 278 3. Testing must be performed no more than 7 days prior to enrollment.

279 If the patient is uncooperative because of resistance to wearing trial frames or using a
280 phoropter, he/she should be given a 15-minute break before attempting to retest. If the
281 patient is still uncooperative and visual acuity is not attainable, the child can not be enrolled
282 in the study at this time. However, the patient may be retested on a different day provided
283 no spectacles are worn in the interim.

284 3. Additional Clinical Testing:

- 285 1. Ocular examination as per investigator's clinical routine to rule out a cause for
286 reduced visual acuity other than amblyopia
 - 287 • If performed within prior 2 months, do not need to repeat at time of enrollment
- 288 2. Cycloplegic refraction using cyclopentolate 1% as per investigator's usual routine
 - 289 • If performed within prior 2 months, do not need to repeat at time of enrollment

290
291 **2.4 Enrollment of Consented Patients**

292 Once the parent(s) of the patient meeting the overall eligibility criteria have given consent to enter
293 the study, the patient will be enrolled in the study using the website study enrollment process.

294 **2.5 Spectacle Correction**

295 The following guidelines apply for prescribing spectacles for all patients who choose to enroll in the
296 study:

- 297 • Full correction of anisometropia
- 298 • Full correction of astigmatism
- 299 • Hyperopia either fully corrected or symmetrically undercorrected by **no more than +0.50D**
- 300 • Bifocals should not be prescribed prior to the Baseline Visit; however, they may be prescribed
301 at any subsequent visit if the esotropia at near exceeds the esotropia at distance after wearing the
302 single vision glasses.

303

304 **2.6 Obtaining Spectacles**

305 Patients who choose to enroll in the study will be sent to a study-certified optician to have the
306 spectacles made.

307

308 The spectacles will either be sent directly to the investigator or picked up by the patient on the day
309 of or day prior to the Baseline Visit. The new spectacles should be carried to the office between
310 pickup and the Baseline Visit. The new spectacles should not be worn prior to the Baseline Visit.

311

312 All enrolled patients will have a Baseline Visit within 30 days of the Screening Visit. The visit
313 needs to be scheduled such that the spectacles prescribed at the Screening Visit will be available, as
314 trial frames are not allowed to be used for visual acuity testing at the Baseline Visit.

315

316 Prior to the Baseline Visit, the office staff should verify that the spectacles prescribed at the
317 Screening Visit have been received or that the patient will be picking them up on the day of the
318 Baseline Visit.

319

CHAPTER 3: BASELINE VISIT

320
321
322
323
324
325
326
327
328
329
330
331
332
333
334
335
336
337
338
339
340
341
342
343
344
345
346
347
348
349
350
351
352
353
354
355
356
357
358
359
360
361
362
363
364
365
366
367

3.1 Baseline Visit

All enrolled patients will have a Baseline Visit within 30 days after the Screening Visit. At this Baseline Visit, the new spectacles with the optimal refractive correction based on the cycloplegic refraction will be placed on the child for the first time.

3.2 Procedures at the Baseline Visit

1. The spectacles prescription should be verified with a lensometer.
 - Sphere and cylinder power must be within 0.25 D of the prescribed correction. Cylinder axis must be within 6 degrees of the axis in the spectacles when cylinder power is >1.00D. If these criteria are not met, the spectacles must be re-made and the patient will return at a later date for the Baseline Visit.
2. The patient should wear the new spectacles for 10 to 30 minutes before the testing in #3-5 below is performed.
3. Visual acuity testing will be done without cycloplegia by a certified examiner using the ATS single-surround HOTV letter protocol on the Electronic Visual Acuity Tester. Both the amblyopic and sound eyes must be retested on the same day with a -1.00D lens over the new spectacles (thus decreasing the chance that any persistent accommodative tone will compromise distance visual acuity and making it more likely that best-corrected visual acuity is measured). Baseline visual acuity is considered the better of the two acuity measures. The protocol for conducting the visual acuity testing is described in the ATS Testing Procedures Manual.
4. Ocular alignment with the cover/uncover test, SPCT, and APCT (*section 2.3.2*) at distance and near is evaluated through the new spectacles.
5. Stereoacuity with the Titmus fly and Randot Preschool Stereoacuity tests

3.3 Visual Acuity Change

3.3.1 Presumed Latent Hyperopia

If visual acuity improves when the child is tested with a -1.00D lens over the spectacles compared to the initial visual acuity measured at the Baseline Visit without the minus lens, the investigator should consider the possibility of persistent accommodative tone and either change the spectacles (if changed, the hypermetropic correction can only be symmetrically undercorrected by no more than 0.50 D from the cycloplegic refraction – *section 2.5*) or wait and allow the patient to relax into them.

- If spectacles are changed (*section 3.3.3*), the patient must return for the Baseline Visit at a later date.
- Investigators may choose not to change spectacles at the Baseline Visit because of the expectation that the patient will relax his/her accommodation over time. However, if the investigator feels that the patient will require assistance relaxing his/her accommodation, the investigator must call the Protocol Chair to discuss management options, which may include bilateral cycloplegia. If the spectacles are not changed, patients will not be required to return for another Baseline Visit; relaxation of accommodative tone will be verified at Visit A (9-week Visit). The visual acuity recorded at the Baseline Visit will be the better of the two acuities (with or without the -1.00D lens over spectacles). If visual acuity at Visit A (9-week Visit) has not improved to be the same or better than the visual acuity obtained using the minus lens at

368 the Baseline Visit, the spectacles should be changed at Visit A according to *section 2.5*
369 if a refraction and visual acuity testing confirm a better visual acuity with a change in
370 refraction.

371 If at the Baseline Visit, the minus lens does not improve visual acuity compared to the initial visual
372 acuity measured at the Baseline Visit without the minus lens, the patient can begin the study unless
373 the investigator suspects an error in refraction, in which case a cycloplegic refraction should be
374 performed. If the original refraction was not correct, the spectacles should be changed (*section*
375 *3.3.3*), and the patient should return for the Baseline Visit at a later date.

376
377 **3.3.2 Other Cases of Reduced Visual Acuity**
378 If at the Baseline Visit, visual acuity with spectacles in either eye is worse than the visual acuity at
379 the Screening Visit with trial frames, the investigator should suspect an error in refraction, and
380 consider a cycloplegic refraction (though not mandated). If performed and the original refraction is
381 not correct, the spectacles should be changed (*section 3.3.3*), and the patient should return for the
382 Baseline Visit at a later date.

383
384 **3.3.3 Changing Spectacles**
385 When spectacles with optimal correction are not available at the Baseline Visit, whether due to the
386 spectacles having been made incorrectly or because a new correction needs to be prescribed, the
387 spectacles should be changed according to the criteria listed in *section 2.5*. The patient should not
388 wear the original spectacles prescribed when enrolled into the study until he or she returns at a later
389 date for the Baseline Visit with the new spectacles. If a spectacle change is required at the Baseline
390 Visit, bifocals should not be prescribed at this time; however, they may be prescribed at any
391 subsequent visit if the esotropia at near exceeds the esotropia at distance after wearing the single
392 vision glasses.

393
394 **3.4 Assessment of Eligibility at Baseline**
395 The patient must have strabismus or a history of strabismus associated with amblyopia (*section 2.2*)
396 at the time of enrollment. Regardless of whether the strabismus remains after wearing the optimal
397 spectacles for 10-30 minutes, the patient will remain in the study provided the patient still meets the
398 eligibility criteria for amblyopia (visual acuity criteria for amblyopic and sound eyes and interocular
399 difference – *section 2.2*) while wearing the spectacles. If the patient has better than 20/40 visual
400 acuity in the amblyopic eye, worse than 20/40 visual acuity in the sound eye, or < 0.3 logMAR
401 interocular difference, the patient is no longer eligible for the study.

402

CHAPTER 4: TREATMENT AND FOLLOW UP

403
404
405
406
407
408
409
410
411
412
413
414
415
416
417
418
419
420
421
422
423
424
425
426
427
428
429
430
431
432
433
434
435
436
437
438
439
440
441
442
443
444
445
446
447
448

4.1 Treatment

Each patient will receive spectacles with his/her optimal correction (*section 2.5*), paid for by the study. No additional treatment will be provided to patients in this study.

- If a patient receives active treatment (e.g., patching, atropine, filters, visual therapy) of any kind, the patient will end study follow-up.
- If glasses are worn prior to the baseline visit for more than one day, the patient will end study follow-up.

4.2 Visit Schedule

- Visit A: 9 weeks \pm 10 days
- Visit B (Outcome examination by ATS certified examiner): 18 weeks \pm 10 days
- 9-week Follow-up Exams (if required- *section 4.5*): every 9 weeks \pm 10 days until amblyopia resolves (amblyopic eye acuity better than or equal to the best sound eye acuity) or until visual acuity in the amblyopic eye does not improve at least 1 line (confirmed by a retest with a -1.00D lens over spectacles) from the previous study visit (either visit B or prior 9-week Follow-up Exam).

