4.3 Testing Procedures

1. Visual acuity testing at all follow-up exams will be done without cycloplegia by a certified examiner using the ATS single-surround HOTV letter protocol on the Electronic Visual Acuity Tester.
 - Amblyopic eye visual acuity must also be retested with a -1.00D lens over the optimal refraction (to account for possible persistent accommodative tone).
 - If the sound eye visual acuity is reduced 1 or more lines from the previous visit, the sound eye must also be retested with a -1.00D lens over the optimal spectacle correction.
 - Follow-up visual acuity is considered the better of the two acuity measures (with and without the -1.00D lens). The protocol for conducting the visual acuity testing is described in the ATS Testing Procedures Manual.
 - For Visit B (18-week outcome exam) and all subsequent exams, if the better of the two visual acuities (with and without the -1.00D lens over spectacles) is not at least 1 line better than the visual acuity from the previous study visit, the study ends for this patient. If the better of the two visual acuities (with and without the -1.00D lens) is at least 1 line better than the visual acuity at the previous study visit, study follow-up continues.
2. Detection of strabismus at distance and near by cover/uncover testing, with measurement of any strabismus using the Simultaneous Prism and Cover Test (SPCT) and the Alternate Prism and Cover Test (APCT) (*section 2.3.2*) is performed through the optimal refractive correction. The SPCT should be performed before the APCT (*section 2.3.2*).
 - If the spectacles are bifocals, ocular alignment at near should be tested through the bifocal portion of the lenses. If necessary, the bifocals should be raised to ensure that the patient is viewing the near target in primary position (not down gaze) while looking through the bifocal lenses.
3. Stereoacuity with the Titmus Fly and Randot Preschool Stereoacuity tests

449 **4.4 Changes in Treatment Prior to the 18-week Outcome Visit**

- 450 • Amblyopia treatment in addition to spectacles (e.g., patching, atropine, vision therapy,
451 filters) is NOT allowed prior to the 18-week outcome exam.
- 452 • If the investigator determines that a spectacle change is required after the child has worn the
453 glasses initially prescribed, spectacles may be changed prior to the 18-week outcome exam.
454 Bifocals may be prescribed at any visit after the Baseline Visit if the esotropia at near

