455 exceeds the esotropia at distance after wearing the single vision glasses.

456 **4.5 Follow-up Exams for Patients Still Improving**

457 Beginning at Visit B (18-week outcome exam) and for subsequent study visits, visual acuity in the
458 amblyopic eye will be classified as “stable” or “improving” based on the following criteria:

- 459 • Vision is considered “stable” when amblyopic eye visual acuity has not improved at least 1 line
460 (confirmed by a retest with a -1.00D lens over spectacles) from the previous study visit (Visit B
461 or subsequent 9-week Follow-up Exam).
- 462 • Vision is “improving” when amblyopic eye visual acuity has improved 1 or more lines from the
463 previous study visit.
- 464
- 465
- 466 ➤ If vision at Visit B (18-week outcome examination) or a subsequent 9-week Follow-up
467 Exam is classified as “stable,” the study is complete for this patient.
- 468 ➤ If vision is classified as “improving,” additional 9-week Follow-up Exams will be scheduled
469 every 9-weeks (± 10 days) until vision is classified as “stable.”

470

471 Testing at each 9-week Follow-up Exam will include the procedures listed in *section 4.3*. (visual
472 acuity, ocular alignment, and stereoacuity).

473 **4.6 Non-study Visits**

474 Non-study Visits may be scheduled at the discretion of the investigator between Visit B (18-week
475 outcome exam) and the first 9-week Follow-up Exam or between any two subsequent 9-week
476 Follow-up Exams. The investigator may discontinue the patient from the study if he or she feels
477 strongly that treatment in addition to spectacles is required.

478

479 Data from Non-study Visits will not be collected. Determination of visual acuity improvement is
480 made based on visual acuity measurements from Visit B (18-week outcome exam) and subsequent
481 9-week Follow-up Exams.

482 **4.7 Treatment Changes Following the 18-week Outcome Visit**

- 483
- 484
- 485 • If the investigator determines that a spectacle change is required, spectacles may be changed
486 following the 18-week outcome exam. Bifocals may be prescribed if the esotropia at near
487 exceeds the esotropia at distance after wearing the single vision glasses.
- 488 • Although discouraged, additional treatment may be started at any 9-week Follow-up exam
489 or Non-study Visit following the 18-week Outcome Visit if the investigator feels strongly
490 that treatment in addition to spectacles is required, even if the visual acuity has improved 1

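### Sections 1.3 and 4.2 end follow-up when amblyopia resolves, but 4.3 and 4.5 continue any child still gaining a line, so a child who resolves while improving gets opposite instructions

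*Protocol*

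**What the plan says.** Four sections of the protocol state when follow-up after the 18-week visit ends.

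- **Section 1.3 (synopsis, visit schedule)** continues the 9-week exams until amblyopia "resolves or until visual acuity does not improve at least 1 line". It refers to 4.5.
- **Section 4.2** has the same two stopping conditions and defines the first: "until amblyopia resolves (amblyopic eye acuity better than or equal to the best sound eye acuity". The comparison for the second is "from the previous study visit (either visit B or prior 9-week Follow-up Exam". It also refers to 4.5.
- **Section 4.3** sets its scope as "For Visit B (18-week outcome exam) and all subsequent exams". If the better of the two acuities "is not at least 1 line better than the visual acuity from the previous study visit, the study ends for this patient". If it "is at least 1 line better than the visual acuity at the previous study visit, study follow-up continues". Resolution is not mentioned.
- **Section 4.5** classifies acuity as *stable* or *improving* from Visit B onward. A stable child is finished; an improving child returns every 9 weeks until stable. Resolution is not mentioned here either. *Stable* means no 1-line gain, "confirmed by a retest with a -1.00D lens over spectacles) from the previous study visit (Visit B" or a subsequent 9-week exam.

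Section 6.1.1 takes each patient's maximum acuity at 18 weeks or later, with the visit at which it occurred, and analyses it in parallel with the 18-week result. Section 6.1.3 uses stereoacuity and alignment at the time of best amblyopic-eye acuity.

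**The concern.** The stopping rule decides how many visits contribute to each child's maximum, so it forms part of the definition of the endpoints in 6.1.1 and 6.1.3. Two sections say that resolution ends follow-up. Two others, including the one to which the first two refer for detail, say that a gain of at least 1 line continues it without exception. The children caught between them are those who respond best to spectacles. If sites follow different sections, two such children may be followed for different lengths of time, and the one seen more often has more chances to record a higher maximum.

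A second, smaller defect is in 4.5. Visit B is classified there, yet the visits listed as possible comparators start at Visit B itself, so read literally Visit B has nothing to be compared with.

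**Working it through.** **1. The four possible outcomes at a visit (Visit B or later), under each pair of sections**

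| Gain of at least 1 line? | Resolved? | 1.3 and 4.2 | 4.3 and 4.5 |
|---|---|---|---|
| No | No | stop | stop |
| No | Yes | stop | stop |
| Yes | No | continue | continue |
| Yes | Yes | **stop** | **continue** |

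Only the last row conflicts, and no reading satisfies both columns.

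**2. The comparator for Visit B.** Section 4.3 applies the 1-line test to Visit B against the previous study visit, which in the schedule of 4.2 is Visit A. Section 4.5 lets a stable Visit B end the study, which requires an earlier visit for comparison. Its definition of *improving* refers to the previous study visit with no parenthesis. Only the parenthesis under *stable* leaves out Visit A. The similar parenthesis in 4.2 governs the 9-week exams alone and is correct there.

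**3. Which results can move.** The 18-week proportion and mean use Visit B only, so neither defect touches them. For the 2-line proportion at maximum acuity, entry needs an inter-eye difference of at least 3 logMAR lines (section 2.2), required again at Baseline (section 3.4). A child who reaches the best sound-eye acuity has therefore normally gained at least 3 lines and counts as a 2-line responder under either rule. What can move is the mean maximum gain, the visit of the maximum, and stereoacuity and alignment at that visit.

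**4. Size of the shift in mean maximum gain.** The protocol gives no measurement error and no share of children who resolve while improving, so both are assumed:

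- s, the SD of one visit's recorded acuity about the child's true acuity: 0.5 to 1.0 line
- f, the share of patients resolved while still improving: 10% to 33%
- one extra visit, with no true change

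The expected excess of the better of two independent normal readings with equal mean is s/√π. The shift in the subgroup mean is f × s/√π.

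| s (lines) | s/√π | f = 0.10 | f = 0.20 | f = 0.33 |
|---|---|---|---|---|
| 0.50 | 0.28 | 0.028 | 0.056 | 0.093 |
| 0.75 | 0.42 | 0.042 | 0.085 | 0.140 |
| 1.00 | 0.56 | 0.056 | 0.113 | 0.186 |

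The range is about 0.03 to 0.19 line. It contrasts every site following one pair of sections with every site following the other; mixed practice falls between.

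**5. Yardstick.** The precision table in section 6.2 gives a half-width of 0.5 line for SD 2.0 and N = 68. This reproduces: 1.96 × 2.0/√68 = 0.475. The shift is thus between 0.028/0.475 = 6% and 0.186/0.475 = 39% of the half-width.

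The calculation is rough. The visit at which a child is found resolved and improving is selected for a good reading, so equal means somewhat overstate the gain from noise alone. True further improvement, or more than one extra visit, would raise it.

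**The case against.** The strongest reply is that the conflict is narrow and the outcome that matters most is safe. A resolved child with no gain stops under every section, the 18-week results do not depend on the rule, and the 2-line proportion hardly moves. All of that stands, and it limits the point. It does not remove the conflict in the last row of the first table, because the analysis of maximum acuity is planned for every patient.

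It may also be said that 4.5 governs, since 1.3 and 4.2 refer to it. That would leave the resolution clause, which 4.2 takes the trouble to define, without effect. The protocol does not say that it should be ignored.

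Three stronger readings are tempting, and the protocol does not support them.

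- *Visit B has no comparator, so every child must return for a further exam.* Section 4.3, the provision in 4.5 for a stable Visit B, and the qualifiers in 1.3 and 4.2 that make the 9-week exams conditional all rule this out. Visit A is the only coherent comparator. Section 4.6, where improvement is "made based on visual acuity measurements from Visit B (18-week outcome exam) and subsequent" exams, might seem to point the other way. It directly follows the statement that Non-study Visit data are not collected, and it serves only to exclude those data.
- *A large share of children is affected, because at least one third resolved in the study cited in section 1.1.* That study enrolled anisometropic children, and the figure counts all who resolved, not those who resolved at a visit with a 1-line gain.
- *Follow-up will differ between sites and the later data will not be comparable.* The text makes divergence possible. It does not show that it will occur.

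**Conclusion.** The contradiction on resolution is real: sections 1.3 and 4.2 on one side and 4.3 and 4.5 on the other give opposite instructions for a child who resolves while still gaining at least 1 line. The Visit B matter is a single incomplete parenthesis in 4.5, not a rival rule. Sites may end follow-up differently for the affected children, with consequences confined to maximum acuity, its timing, and stereoacuity and alignment at best acuity. The estimated shift in mean maximum gain is modest, and it rests on an error SD and an affected share that the protocol does not supply. The case for acting is that the rule helps define a stated endpoint and the repair is simple.

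**What to change.** Reconcile sections 1.3, 4.2, 4.3 and 4.5 into one continuation rule, worded identically in each, that says explicitly whether resolution ends follow-up. Correct the parenthesis under *stable* in 4.5 so that Visit B has a named comparator consistent with 4.3. Which rule to adopt is for the sponsor to decide. The cost is a wording change in four sections and a short notice to sites; sample size, visit windows and the 18-week analysis do not change.
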